11. One year follow-up data including assessments of cognitive function (Short Blessed Test), activities of daily living, and depression (Center for Epidemiologic Studies-Depression (CES-D) test will be obtained by phone interview, and we will examine the clinical chart for admissions, events (any renal replacement therapy), and laboratory findings (with particular focus on serum creatinine, eGFR, and urine proteinuria) in this period.
12. Safety endpoints will focus on any risk of hypoxia between study groups and will include postoperative day 1 serum CK-MB measurements (myocardial injury, defined as CK-MB greater than 50 ng/mL [10 times the upper limit of normal] and CK-MB as a continuous endpoint), postoperative myocardial infarction [defined by a new Q-wave on EKG], rates of reintubation, transient ischemic attack [defined as new deficit on neurologic exam that abates within 72 hours], stroke [defined as new deficit on neurologic exam and confirmed with radiological evidence], and death.

Urine, blood, and tissue use:

Following the placement of the arterial line and Foley catheter, 20 mL of blood and 20 mL of urine will be collected at the induction of anesthesia (baseline). We will also collect 15 mL blood and 20 mL of urine during cardiopulmonary bypass or off-pump coronary artery bypass for those subjects not requiring cardiopulmonary bypass, following cardiopulmonary bypass or off-pump coronary artery bypass, at ICU admission, 6 hours after ICU admission, and on postoperative day 1 and day 2. In total we will collect 110 mL of blood and 140 mL urine. When, after dissection of the pericardial fat, mammary artery, and incision of the atria as part of standard cardiac surgery, 1-2 g of redundant atrial tissue, 1-2 grams of discarded fat, and 1-2 g of discarded distal mammary artery will be collected for measurement of atrial myocardial function, inflammation, amyloid, oxidative stress, and arteriole vascular reactivity. Typically, this tissue is discarded, but instead we will harvest this tissue at the end of surgery. We used the same technique for collection of tissue in 450 cardiac surgery subjects in the Atrial Fibrillation and Renin Angiotensin Aldosterone System (RAAS) study (PI: [name]).²⁶

We will also collect data regarding vital signs, electroencephalographic activity, medication use, fluid input and urine output, clinical labs, and postoperative outcomes.

Sample Time-course:

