The DSMB will receive report on the progress, adverse events, safety endpoints, and clinical outcomes at each interim analysis from the PI and the statistician. The first planned interim analyses will occur after 20 (11.1%) subjects have been studied and discharged from the hospital following surgery. At this meeting, the DSMB will evaluate subject recruitment, the documentation of subject data, and the collection and reporting of adverse events, serious adverse events, and safety endpoints. The DSMB will also evaluate any study withdrawals, any adverse events, in-hospital all-cause mortality, and safety outcomes (stroke, TIA, or Q-wave myocardial infarction).

The second planned interim analyses will occur after 100 (50%) subjects have been studied and discharged from the hospital following surgery. At this meeting, the DSMB will evaluate any study withdrawals, any adverse events, in-hospital all-cause mortality, safety outcomes (stroke, TIA, or Q-wave myocardial infarction), and a conditional power analysis implemented by the study statistician. The conditional power analysis will assess the likelihood of rejecting the null hypotheses (for the primary endpoints of Aims 1 and 2) at the study conclusion (N=200), assuming that the effect of intervention is as large or larger than the estimated effect at the second interim analysis (N=100). To do so, the study statistician will compare mock-unblinded data (A vs. B, where it remains unknown if A or B is normoxia or

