We have recruited an experienced and versatile DSMB to help us carefully monitor the safety and efficacy of subject treatment. At either planned interim analysis the DSMB may recommend to continue enrollment and subject study or suspend enrollment and subject study due to safety concerns secondary to study intervention including: increased in-hospital all-cause mortality in subjects randomized to physiologic oxygenation (normoxia) such that the DSMB deems the increase is excessive compared to usual care hyperoxic oxygenation (hyperoxia), increased SAEs deemed "Probably Related" or "Possibly Related" to study intervention in physiologic oxygenation (normoxia) group compared to usual care hyperoxic oxygenation (hyperoxia) group deemed excessive, or increased incidence of stroke, TIA, or Q-wave myocardial infarction in the physiologic oxygenation (normoxia) group compared to usual care hyperoxic oxygenation (hyperoxia) group deemed excessive. The DSMB will require strong statistical evidence, corresponding to a p-value threshold of 0.001, to end the trial early due to safety concerns. The DSMB will not make any recommendations to end the study early due to efficacy or futility.

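### As defined, TIA and stroke both miss a lasting deficit without imaging confirmation, and both capture a brief deficit with it

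*Combined protocol and SAP*

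**What the plan says.** Section 6.0 (Study Procedures), endpoint 12, lists the safety endpoints meant to detect harm from hypoxia and gives the only definitions of the two neurologic events:

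- TIA: "new deficit on neurologic exam that abates within 72 hours". There is no imaging condition, positive or negative.
- Stroke: "new deficit on neurologic exam and confirmed with radiological evidence". There is no duration condition.

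The labels are used in three places:

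- In the Data and Safety Monitoring Board (DSMB) part of section 6.0, the interim reviews cover "safety outcomes (stroke, TIA, or Q-wave myocardial infarction", so stroke and TIA are two of the three named outcomes.
- In the same part, one ground for suspending the study is an "increased incidence of stroke, TIA, or Q-wave myocardial infarction in the physiologic oxygenation (normoxia) group". Ending early needs strong evidence, "corresponding to a p-value threshold of 0.001, to end the trial early due to safety concerns".
- In section 10.0 (Data Analysis Plan), TIA and stroke are compared between arms as safety endpoints, and stroke also appears among the secondary endpoints.

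Section 8.0 separately defines adverse events broadly. It counts an event as serious if, among other things, it prolongs the hospital stay or leaves lasting or substantial disability.

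**The concern.** Two labels that rest on different criteria, one on time and one on imaging, do not divide up all new deficits. Whether a lasting deficit counts depends on whether a scan was done and was positive. The protocol does not require a scan for a new deficit, and section 6.0 leaves postoperative care to the clinical team. As the wording stands, a deficit that clears within three days counts in the neurologic safety outcome, while one that persists without confirmation does not.

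The trial compares lower with higher oxygen exposure, and these endpoints are there to show whether the lower exposure does harm. At stake is whether the stroke and TIA tables shown to the DSMB and in the final report include every patient with a new deficit, under a rule fixed before treatment assignments are known.

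**Working it through.** The plan states no figure on this point, so there is none to reproduce. The check crosses the two criteria in endpoint 12.

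| New deficit | Imaging confirms | Meets TIA | Meets stroke | Labels |
|---|---|---|---|---|
| Gone within 72 h | No or not done | Yes | No | 1 |
| Lasts beyond 72 h | Yes | No | Yes | 1 |
| Gone within 72 h | Yes | Yes | Yes | 2 |
| Lasts beyond 72 h | No or not done | No | No | 0 |

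Of the four cells, one has no label and one has two.

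**Does another section resolve it?** Section 5.0 says that blinded physicians and research staff measure the clinical endpoints, but it describes no adjudication of neurologic events. Sections 6.0 and 10.0 give no order of precedence and no residual category.

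**Is the unlabelled patient caught elsewhere?** In part.

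- Under section 8.0 the deficit is an adverse event and may well be serious. The DSMB reviews adverse events at its interim meetings.
- A patient who dies before a scan is counted as a death, and in-hospital mortality is a separate suspension ground.
- The suspension ground based on serious adverse events is limited to those judged possibly or probably related to the intervention. The stroke/TIA ground has no such condition. A persistent, unconfirmed deficit judged unlikely to be related, in a survivor, falls under neither.
- Adverse event reporting does not put the patient back into the stroke and TIA comparison in section 10.0.

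**Size of one case.** "The second planned interim analyses will occur after 100 (50%) subjects have been studied and discharged". With equal allocation (assumed), that is 100 / 2 = 50 per arm, and one patient is 1/50 = 2 percentage points. At 200 subjects it is 1/100 = 1 point.

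**Could one case cross the 0.001 threshold?** The DSMB's test is not named, so a two-sided Fisher exact test is assumed. With k events in one arm of 50 and none in the other, p = 2 × C(50,k) / C(100,k).

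| Split at 50 per arm | p |
|---|---|
| 6 vs 0 | 0.027 |
| 10 vs 0 | 0.0012 |
| 11 vs 0 | 0.0005 |

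With no events in the other arm, one missing patient decides the matter only between 10 and 11 events, that is 10/50 = 20% and 11/50 = 22% of an arm. The formal threshold is therefore not where the gap is likely to bite. Its effect is on what the tables show and what the DSMB weighs.

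**The case against.** The strongest reply is that no event disappears. A lasting deficit would be an adverse event and probably a serious one, the DSMB sees adverse events, and deaths are counted. The suspension grounds are given as examples and turn on what the DSMB considers excessive, so it could act on such a case anyway. This largely stands. A reader might infer that these patients vanish from safety monitoring, and the documents do not support that. What remains is narrower: they are absent from the stroke/TIA criterion and from the final comparison, and the serious-event ground, limited by attribution, is not an equivalent substitute.

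A reader might also infer that the overlap inflates the counts. It does not. In separate rates the patient appears once in each; in an either/or outcome per patient, once overall. No section adds the two rates. The overlap is only an unstated order of precedence.

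Nor do the documents support putting a percentage on the strokes missed. That needs an event rate and the share of persistent deficits that go unconfirmed, and neither is given. No bias between arms is shown either: ICU staff and endpoint assessors are blinded, so misclassification would be expected to be similar in both.

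Finally, requiring imaging for stroke is a legitimate choice in favour of specificity, and calling every persistent scan-negative deficit a stroke would admit other causes. That is accepted, and the fix leaves the stroke definition alone.

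**Conclusion.** The point holds as a gap in the definitions. Read as written, TIA and stroke are neither exhaustive nor mutually exclusive, and no other section repairs this. A new deficit lasting beyond 72 hours without imaging confirmation is left out of the stroke/TIA safety endpoint, the matching suspension criterion and the final comparison, though it is still recorded as an adverse event or death. A deficit that resolves within 72 hours with positive imaging meets both definitions.

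The conclusion rests only on the wording of endpoint 12. The 2-point figure also assumes equal allocation, and the p-values assume a Fisher test. The frequency of such cases cannot be estimated from the documents. No primary endpoint, sample size or power figure is affected. This is a minor clarification, worth making because it costs almost nothing and the present rule counts a transient deficit while omitting a lasting one.

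**What to change.** Amend endpoint 12 in section 6.0 and the safety paragraph of section 10.0, before treatment assignments are unblinded:

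1. Keep stroke as defined, with imaging confirmation.
2. State that stroke takes precedence when a patient meets both definitions, so that TIA means a deficit resolved within 72 hours without positive imaging.
3. Add a third category, *persistent new deficit without imaging confirmation*, covering a negative scan, no scan, or death before a scan.
4. Report by arm, to the DSMB and in the final safety analysis, the number of patients with *any new neurologic deficit*, each counted once, beside the separate categories.

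Section 10.0 already provides Fisher's exact or the chi-square test for such counts. How the DSMB weighs the third category under its suspension criteria is for the DSMB and the investigators to state.

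The cost is a few sentences and one more row in the safety tables, with no new procedure. The small downside is that the combined count is less specific, because it may include deficits that are not ischemic; showing the categories separately keeps that visible.

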hyperoxia). If the conditional power is less than the original target (80%), the DSMB will consider recommending an increase in the study sample size to achieve the target power. If an increased sample size is determined to be reasonable by the investigators within the study constraints including feasibility and funding, we will seek approval from the VU IRB to increase the sample size. If the sample size is increased based on the conditional power analysis, an additional interim analysis will be scheduled to occur after 200 subjects have been studied and discharged from the hospital after surgery. At this interim analysis meeting (N=200), the DSMB will evaluate safety by analyzing any study withdrawals, any adverse events, in-hospital all-cause mortality, safety outcomes (stroke, TIA, or Q-wave myocardial infarction), and the unblinded treatment effect on the primary endpoint of Aim 1 (previously only assessed in a mock-unblinded manner for the purpose of conditional power analysis). This analysis will be completed to assess safety not efficacy of the intervention. However, if the sample size is increased, then the statistical significance thresholds for the final analyses will be adjusted to preserve the overall type-I error rate at 5%. For example, if the sample size is increased to 300, then the p-value threshold at the final analysis (for the primary aim using the Wilcoxon rank sum test) will be 0.0499 to preserve the overall type-I error probability at 5%.

There will be no possibility of ending the trial early due to futility or efficacy. All investigators and research personnel (other than the study statistician at the second interim analysis) will remain blinded to treatment assignment during all interim analyses.

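### The 5% type I error promised after a sample-size increase at N=100 is not guaranteed: the increase rule is incomplete, and 0.0499 appears to correct only for the added look at N=200

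*Combined protocol and SAP*

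**What the plan says.** All of this is in Section 6.0 under the Data and Safety Monitoring Board, unless noted.

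- **What is computed at N=100.** The calculation "will assess the likelihood of rejecting the null hypotheses (for the primary endpoints of Aims 1 and 2) at the study conclusion (N=200"). It takes the observed effect as its premise, "assuming that the effect of intervention is as large or larger than the estimated effect at the second interim analysis". The statistician works with arms labelled A and B, without knowing which is which.
- **What can follow.** "If the conditional power is less than the original target (80%), the DSMB will consider recommending an increase in the study sample size". The stated purpose is "an increase in the study sample size to achieve the target power". The increase must be "determined to be reasonable by the investigators within the study constraints including feasibility and funding", and needs IRB approval.
- **What an increase adds.** There is a further look at N=200 that includes the unblinded Aim 1 effect. Of this look the plan says "This analysis will be completed to assess safety not efficacy of the intervention".
- **The error promise.** If N is increased, "then the statistical significance thresholds for the final analyses will be adjusted to preserve the overall type-I error rate at 5" per cent. The example is N=300, where the Wilcoxon threshold "will be 0.0499 to preserve the overall type-I error probability at 5" per cent.
- **Stopping.** Stopping for futility or efficacy is excluded. A p-value of 0.001 is required to stop for safety.
- **Final tests.** Section 10.0 (Data Analysis Plan) specifies the ordinary Wilcoxon test for Aim 1 and a mixed model for Aim 2. No weighted or combination statistic appears.

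**The concern.** The new N would be chosen from the treatment comparison itself. Masking the labels does not change this: two-sided conditional power depends on the size of the A-versus-B difference, which the statistician sees, and not on its direction.

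When N depends on the interim effect, the ordinary test on the pooled data no longer holds its nominal level under every rule. Adding patients after a weak interim result dilutes that result and raises the chance of a false rejection. Adding them after a promising result does not. The outcome therefore turns on which interim results lead to an increase, and the plan gives no lower limit on conditional power, no numerical maximum N and no rule for when the two aims disagree. With no futility stop, weak results remain eligible.

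At stake is an explicit 5% promise on the primary endpoint. If the rule is settled only after the N=100 effect is known, a reader cannot check that the threshold was adequate.

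**Working it through.** **Inputs.** Two-sided 0.05; N=200 for 80% power at 0.15 ± 0.375 mg/dl; Aim 2 planned difference 20 ± 50 pg/ml and pilot 35 ± 30 pg/ml (Section 10.0). Interim at 100, trigger 80%, added look at 200, example N=300 at 0.0499, safety threshold 0.001 (Section 6.0). Assumed: 1:1 allocation, no dropout, normal approximation, conditional power at the observed effect.

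**1. The plan's own figures.**
- Power at N=200: (0.15/0.375) × √(200/4) = 2.828; Φ(2.828 − 1.960) = 80.7%, as stated.
- 0.0499: take a two-sided p<0.001 look (|z|>3.291) at information 200/300, correlation √(2/3), and solve for the final critical value giving 5% overall. The final p is 0.04994. An O'Brien-Fleming boundary at the same timing gives 0.0452 and does not fit.

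**2. When the trigger fires.** With interim statistic z and t = 100/N, conditional power at the observed effect is Φ[(|z|/√t − c)/√(1−t)] plus a negligible opposite tail. For N=200 (t=0.5, c=1.960) it reaches 80% at |z|=1.807, 50% at 1.386 and 20% at 0.965. Under the null, P(|z|<1.807) = 92.9%, so the trigger is the usual case. Under the planned effect (interim mean 0.4 × √(100/4) = 2.0) it is 42.3%.

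**3. Why weak results matter.** Given z, the null chance of rejecting at final N is Φ[(√t·z − c)/√(1−t)] + Φ[(−√t·z − c)/√(1−t)].

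| Interim z | Stay at 200 | Go to 300 at 0.0499 |
|---|---|---|
| 0.5 | 1.21% | 2.32% |
| 0.965 | 3.55% | 4.38% |
| 1.386 | 8.29% | 7.80% |

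The two are equal at z=1.276, where conditional power is about 41%. An increase below that adds error; an increase above it removes some.

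**4. Overall Aim 1 error** (step 3 integrated over z under the null; Aim 1 alone drives the decision):

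| Rule | Max 300 | Max 400* | Max 600* |
|---|---|---|---|
| To the maximum whenever conditional power <80% | 5.61% | 5.89% | 6.17% |
| Raise to 80% power or the maximum | 5.67% | 6.05% | 6.47% |
| Worst case under full discretion | 5.78% | 6.19% | 6.62% |
| Raise only if 80% is attainable | 4.94% | 4.88% | 4.87% |

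*Assumed maximums; the plan names only 300.

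Under the first rule the threshold at N=300 would have to be about 0.042. Wilcoxon simulation of that rule gave 5.64% (200,000 null runs) and 5.5% (a separate 60,000), against 5.00% and 4.9% at fixed N=200.

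**5. Combining the aims** (N=300, independent endpoints, Aim 2 simplified to a two-group z). Let p be the chance that Aim 2 is below 80%: 92.9% with no Aim 2 effect; 42.3% with 20/50, where the interim mean is 0.4 × 5 = 2.0; about 0 with 35/30, treating 30 as the SD. If either aim triggers, Aim 1 error is p × 4.99% + (1−p) × 5.61% = 5.03%, 5.35% and 5.61%. If both must trigger, it is p × 5.61% + (1−p) × 5.00% = 5.56%, 5.26% and 5.00%. The missing combination rule alone moves the error between 5.0% and 5.6%.

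**The case against.** The strongest reply is that the plan allows an increase only to reach the target power, subject to three layers of judgement. Most of the excess comes from increases that could not serve that purpose. With a maximum of 300, excluding increases below 20% conditional power cuts the worst case from 5.78% to 5.07%. On the natural reading, with N raised only when 80% is attainable, there is no excess at maximums of 300, 400 or 600.

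This stands as a limit on size and likelihood. It does not restore the guarantee. What is attainable is undefined without a maximum N, and the reading itself depends on one: its error is 5.01% at an assumed maximum of 1000 and 5.39% at 2000. Discretion means the error can be bounded but not verified.

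A second reply is that 0.0499 is only an example and can be reproduced from the plan's own 0.001 threshold and N=200 look. That is fair. A reader might infer that 0.0499 is arbitrary or miscalculated, and the documents do not support this. The link to 0.001 is still an inference, because the plan ties that threshold to safety stopping and does not write out the derivation.

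A reader might also suspect the N=200 look. It is not the source of the excess: that look costs almost nothing, and the issue is the choice of N at 100.

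**Conclusion.** The point holds as an incomplete specification behind an explicit promise. As written, the plan permits increase rules under which the ordinary Wilcoxon test at 0.0499 exceeds 5%: about 5.6%, at worst 5.8%, at the plan's own example of N=300. It equally permits rules that stay at or below 5%. If 0.0499 has the basis that its value suggests, it pays for the N=200 look only.

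A reader might infer that the trial's error rate is inflated, or that it exceeds 6%. The documents do not support either. No rule is stated from which an actual rate could be computed, and figures above 5.8% need maximums that the plan does not name.

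The sizes rest on the assumptions listed with the inputs, supported by Wilcoxon simulation at N=300. Type I error for Aim 2 itself was not computed. The matter is worth correcting because the remedy is cheap and must precede the N=100 data.

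**What to change.** Write the following into the SAP and DSMB wording before the N=100 data are seen.

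1. **Aim 1.** If N is increased, test with the inverse-normal (Cui-Hung-Wang) combination (z₁ + z₂)/√2. Here z₁ is the Wilcoxon z-score from the first 100 patients and z₂ that from all later patients, with weights fixed in advance. Use two-sided 0.05, or the slightly lower level if the correction for the N=200 look is kept. This holds for any increase rule; simulation gave 5.04% and 4.9%.
2. **Aim 2.** Apply the same fixed-weight combination to stage-wise estimates from the mixed model.
3. **Decision rule.** State which aim or aims drive the increase, and what happens when they disagree.
4. **The 0.0499 sentence.** Replace it, or say that it corrects only for the N=200 look.

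The cost is wording and about one point of power: 90.3% versus 91.4% for the ordinary test, under the planned effect with N=300 whenever conditional power is below 80%.

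A valid alternative keeps the ordinary test, with a stated maximum N and increases only when conditional power is at least 50%. That floor is stricter than N=300 needs (about 41%), and it gives up most of the gain from adapting. Power at N=300 is about 83.0% with the floor on Aim 1 only. With the floor on both aims it is 82.4% (planned Aim 2 effect) or 81.1% (no Aim 2 effect), against 80.7% at fixed N=200. The two-aim figures assume independent endpoints and an increase triggered by Aim 1.

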Adverse events (AE) will be monitored by the PI and his staff. An AE is defined as any untoward medical occurrence in a subject, not necessarily having a causal relationship with the study. A serious AE (SAE) is defined as any untoward medical occurrence that a) results in death, b) is life-threatening, c) requires inpatient hospitalization or prolongation of existing hospitalization, d) results in persistent or significant disability/incapacity, or e) is a congenital anomaly/birth defect. AEs will be graded as a) Mild (no limitation of usual activities), b) Moderate (some limitation), or c) Severe (inability to carry out usual activities) and attributed according to the relationship to the study drug and/or procedures as a) Not related, b) Unlikely Related, c) Possibly Related, d) Probably Related, or e) Definitely Related. AEs will be submitted to the IRB as per IRB regulation. Specifically, any SAE determined to be possibly, probably, or definitely related to study participation will be reported to the data safety monitoring board (DSMB) and the IRB within 10 working days of the PI's notification of the event (as per IRB standards). Summary reports of any previously unreported SAEs will be reported to the IRB annually and to the DSMB at interim analyses and as requested. These reports will contain the number of SAEs, a description of each SAE, the category of each SAE, and the relationship of each SAE to study participation. Appropriate changes will be made to the consent form as required.

Summary Reports will be submitted to the IRB at least annually and will contain a) The number of adverse events and an explanation of how each event was handled, b) The number of complaints and how each complaint was handled, and c) The number of subject withdrawals and an explanation of why the subject withdrew or was withdrawn.

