10.0 Statistical Analysis Plan

The primary objective of the analysis will be to compare the effect of intraoperative oxygenation on oxidative damage and organ injury. The primary endpoint of Aim 1 will be change in serum creatinine from baseline (defined as the most recent creatinine measured prior to surgery) to postoperative day 2. The primary endpoint of Aim 2 will be F₂-isoprostanes/isofurans measured in plasma.

Sample Size Calculations

We calculated the subject sample size based on data from the Vanderbilt Statin AKI Cardiac Surgery RCT (PI: [name]).²⁷ Data from this study indicate that mean serum creatinine concentrations increase 0.08 ± 0.37 mg/dl from baseline to postoperative day 2. We have powered the present randomized clinical trial conservatively, particularly since consensus criteria for AKI diagnosis define AKI as a 0.3 mg/dl rise in serum creatinine from baseline to postoperative day 2.²⁹ With 200 subjects, we will have 80% power to detect a 0.15 ± 0.375 mg/dl difference in serum creatinine between groups, with a type I error rate of 5%. In addition, with 200 subjects we will have 80% power to detect a 20 ± 50 pg/ml difference in plasma F₂-isoprostanes between groups, and we observed that physiologic oxygenation was associated with 35 ± 30 pg/ml less increase in plasma concentrations of F₂-isoprostanes among pilot subjects compared to hyper-oxygenated subjects. To account for a potential dropout rate of 10%, we plan to recruit 222 subjects.

For the endothelial function sub-study, we calculated the sample size based on a prior study of patients administered an oral antioxidant, treatment improved FMD 2.3% more than placebo with a standard deviation of 2.0%.³⁰ With 80 patients, we will have greater than 80% power to detect a 2%

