Every effort will be made to avoid missing data. Any methods of missing data imputation (e.g. multiple imputation using the chained-equations method) will be used cautiously as sensitivity analyses; and the analysis of results with imputation would be interpreted in the context of corroboration with the analyses without imputation. The primary analysis will be intention-to-treat. Before data unblinding, [name] will examine any protocol deviations and identify a list of protocol violators. In addition to the intention-to-treat analysis, a secondary per-protocol analysis will be conducted.

Specific inferences on the effects of interest will be made by reporting point estimates, along with 95% confidence intervals. Hypotheses will be tested at a two-sided significance level of $\alpha=0.05$. This data analysis plan will be carried out using the statistical analysis package R (R Development Core Team).

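### Unless the sample size is increased, no by-arm safety review is scheduled after 100 subjects, and deaths, strokes, TIAs and Q-wave infarctions not judged related reach the DSMB only at looks or on its own request

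*Combined protocol and SAP*

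**What the plan says.** **Looks.** Section 6.0 (Data and Safety Monitoring Board) plans a first look after 20 subjects and then: "The second planned interim analyses will occur after 100 (50%) subjects have been studied and discharged from the hospital following surgery". A further look, at 200, is scheduled only if the sample size is raised after the conditional power analysis. It would cover withdrawals, adverse events, in-hospital mortality, stroke, TIA, Q-wave infarction and the unblinded Aim 1 effect.

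**Power to suspend.** The same section states: "At either planned interim analysis the DSMB may recommend to continue enrollment and subject study or suspend enrollment". The grounds are an excess in the physiologic oxygenation arm of in-hospital death from any cause, of SAEs thought possibly or probably related, or of stroke, TIA or Q-wave infarction. Ending the trial early for safety needs evidence at about p = 0.001. A suspension rests on the DSMB judging the excess too large.

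**Reporting.** Section 8.0 gives two routes. On the fast one, "any SAE determined to be possibly, probably, or definitely related to study participation will be reported to the data safety monitoring board" and to the IRB, within 10 working days. Other SAEs go in summary to the IRB annually "and to the DSMB at interim analyses and as requested". The listed contents are number, description, category and relationship to participation. Treatment arm is not listed.

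**Sample size.** Section 10.0: "With 200 subjects, we will have 80% power to detect a 0.15 ± 0.375 mg/dl difference in serum creatinine between groups", and "To account for a potential dropout rate of 10%, we plan to recruit 222 subjects".

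**The concern.** The triggers and the reporting rule use different criteria. Death, stroke, TIA and Q-wave infarction count toward suspension whatever their cause, because the question is whether one arm has more of them. Fast reporting depends instead on a judgement, case by case, that the event may be related to the study. Section 5.0 withholds the treatment key from investigators until the dataset is locked, so that judgement is made without the by-arm comparison on which the triggers rest.

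Up to subject 100 the scheduled looks make up for this. After that, whether another look takes place depends on a conditional power result for efficacy, and then on feasibility, funding and IRB approval. If the trial stays at 200, an excess of unattributed events among later subjects has no scheduled route to a by-arm safety comparison before the end. Section 7.0 says that the intervention may raise the risk of hypoxemia, and that prolonged severe hypoxemia may cause organ infarction, coma and death. These are the harms that the triggers are meant to catch.

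**Working it through.** **1. The plan's own figures.** Inputs from Section 10.0: difference 0.15 mg/dl, SD 0.375, power 80%, "with a type I error rate of 5"%, and from the Data Analysis Plan "Hypotheses will be tested at a two-sided significance level of" 0.05.

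- n per arm = 2 × (1.96 + 0.842)² × (0.375/0.15)² = 98.1, rounded up to 99, or 198 in total. The plan's 200 is reproduced.
- Recruitment: 200/(1 − 0.10) = 222.2, against 222 stated.
- Second look: 100/200 = 50%, as stated.
- First look: 20/200 = 10%. The stated 11.1% fits 20/180. Nothing below depends on it.

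**2. Share treated after the last scheduled look.**

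| Case | Last look | Treated after it |
|---|---|---|
| N = 200, not increased | 100 | 100/200 = 50% |
| 222 recruited, not increased | 100 | 122/222 = 55% |
| Increased to 250 (illustration) | 200 | 50/250 = 20% |
| Increased to 300 (the plan's example) | 200 | 100/300 = 33% |

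The 55% counts the 100 among all those recruited. If the 100 are completers only, about 100/0.90 = 111 will have been recruited by then, and the share is 111/222 = 50%. The look is counted in discharged subjects and no pause in enrolment is stated, so the share treated after the review itself would be somewhat higher.

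**3. Triggers against reporting routes.**

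| Event | Suspension trigger | Route to the DSMB |
|---|---|---|
| SAE judged possibly or probably related | Yes | 10 working days |
| In-hospital death, stroke, TIA or Q-wave infarction, judged unrelated or unlikely related | Yes | At a look, or if the DSMB asks |

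After subject 100, with N unchanged, only the request remains for the second row. No event or date is given that would prompt one.

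**4. What the p < 0.001 rule can detect.** Two-sided Fisher's exact test, equal arms. The smallest splits that cross are 11 v 0 or 13 v 1 events at 50 per arm, and 11 v 0 or 14 v 1 at 75 or at 100 per arm. The documents give no rates for these events, so the rates below are assumptions. The chance of crossing is the sum of the two-binomial probabilities over all crossing tables:

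| Assumed rates | 50 per arm (look at 100) | 75 per arm (a look at 150) | 100 per arm |
|---|---|---|---|
| 3% v 10% | 0.2% | 1.7% | 5.0% |
| 5% v 15% | 1.7% | 5.4% | 12.2% |
| 5% v 20% | 8.9% | 22.5% | 41.4% |

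The look at 100 would seldom meet the formal threshold even under large harm. A look at 150 would not often meet it either.

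**The case against.** The case on the other side has several good parts.

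- A reader might infer that unattributed events reach the DSMB only at looks. Section 8.0 does not support that, since the DSMB may also request them. This stands. The remaining weakness is that the DSMB would have to ask about events it has not been told of, and that arm is not in the listed contents.
- A reader might infer that subjects after 100 are never compared by arm while the trial can still be stopped. That fails if the sample size is increased, because a look at 200 covering the same safety outcomes is then scheduled.
- A reader might infer that the DSMB is barred from acting between looks. Section 6.0 says what it may recommend at a planned look and does not forbid a recommendation at another time. The text is unclear on this; it is not a prohibition.
- The fast route has a low bar, since possibly related is enough, and the IRB sees other SAEs annually. Nothing in the documents shows that this team would attribute events too narrowly. Both points stand, but neither gives the DSMB a by-arm comparison.
- The number of looks is a design choice, and an extra one would rarely end the trial under p < 0.001. The calculation confirms this, so the extra look is not needed for the point to hold. The threshold governs ending the trial, however. Suspension on a judged excess has no such bar and can use timely data.

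**Conclusion.** The gap is real and limited. If the sample size is not increased, no by-arm safety review is scheduled after 100 subjects, and at least 50% of 200 (up to 55% of the 222 recruited) are treated after that look. In that period, deaths, strokes, TIAs and Q-wave infarctions judged unrelated or unlikely related reach the DSMB only on its own request, although they count toward suspension regardless of attribution.

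The conclusion rests on the text of Sections 6.0 and 8.0 and on simple counts. It does not depend on any assumed event rate; those rates serve only to judge what another look would add. The documents do not support a count of excess events, because they give no rates for these outcomes. The point does not affect the validity of the efficacy analysis. It is a safety-reporting mismatch that is cheap to correct and should be corrected.

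**What to change.** 1. **Section 8.0.** Report every death, stroke, TIA and Q-wave infarction to the DSMB within the existing 10 working days, whatever the attribution. Have the study statistician supply the arm to the DSMB in coded form, so that investigators stay blinded.
2. **Section 6.0.** Reword the opening of the suspension sentence so that the DSMB may make its recommendation at any time, including the planned interim analyses.

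The cost is two edits and a few extra reports. Neither change adds an efficacy comparison, so the type I error of the primary analyses is untouched.

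**Optional.** Rerun the existing safety tables, with no efficacy endpoint, at about 150 subjects. The share treated after the last look would fall to 50/200 = 25%, or 72/222 = 32%. The cost is one more run of existing tables and a short DSMB meeting. Under the assumed rates it would cross p < 0.001 in 1.7% to 22.5% of cases, so its value lies mainly in informing a suspension for an excess that the DSMB judges too large.
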